### 2.5.3 Secondary Analyses

Recovery of Cognition: Principal measures of performance are based on preliminary data(Basner, Savitt et al. 2015) of the Cognition test battery. Additional measures include: PVT response speed, DSST throughput, PVT lapses, VOLT duration and accuracy, AM duration and accuracy, and DSST errors. Cognition performance measures associated with lower effect sizes will also be assessed. These include AM accuracy, VOLT accuracy, F2B reaction time, MPT accuracy, MPT duration, and F2B accuracy. Overall, we expect F2B, VOLT, and AMT to recover the slowest due to taxing of short-term memory after ketamine + ECT compared to ketamine + sham ECT.

Recovery in the Spontaneous EEG: We will evaluate mixed-effects models to test the hypotheses that the predominance of frontal delta or theta power during passive eyes opening or occipital alpha power during eyes closed predict cognitive performance (Cognition scores) or delirium (3D-CAM scores). We will also compare these EEG spectral measures across treatment sessions to evaluate the impact of anesthetic and ECT. Relationship of ECT Seizure Duration to Return of Responsiveness to Verbal Command: We expect that the length of ECT-induced seizures will correlate with the intervals from the loss of responsiveness to the return of responsiveness.

Mood and Depression Severity: We expect improvement in these clinical outcomes to be greatest with ketamine + ECT, followed by etomidate + ECT, and then ketamine + sham ECT.

16

Treatment Satisfaction: We expect satisfaction to be greatest for ketamine + ECT, followed by ketamine + sham ECT, and then by etomidate + ECT.

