#### 2.1.2 EEG Activity and Cognitive Dysfunction Following ECT

The potential of EEG to inform clinicians on the future efficacy and side effects of ECT has not been fully realized. EEG is commonly monitored during ECT, a proven treatment for depression, bipolar illness, and psychosis(Lisanby 2007). Following the delivery of the ECT stimulus charge, epileptiform activity in the bilateral fronto-mastoid EEG can complement the assessment of peripheral tonic-clonic muscle activity(Fink and Johnson 1982). Clinically relevant EEG measures beyond the length of seizure duration(Mayur 2006) have unclear clinical utility(Dinwiddie, Glick et al. 2012). Optimally, EEG markers would be available for predicting and refining ECT administration to balance efficacy and side effects that accrue over the course of therapy. Such advances in the field have not occurred since prior work establishing a relationship between cognitive performance and ECT stimulation parameters(Weiner, Rogers et al. 1986, Abrams 2002). This void may be due to the paucity of studies that have characterized EEG across widely distributed brain regions using either 10-20 montages(Brumback and Staton 1982, Luber, Nobler et al. 2000, Nobler, Luber et al. 2000, Zoldi, Krystal et al. 2000) or high-density EEG. The spatial resolution offered by high-density EEG is likely needed to associate cognitive an affective perturbations to specific EEG patterns. High-density scalp EEG has shown superiority over standard 10-20 montage recordings in guiding surgical treatment for epileptic seizures (Brodbeck, Spinelli et al. 2011). Extension of this paradigm to the ECT setting may yield clinically relevant EEG markers for tailoring treatment at an individual patient level.

During the ictal period, seeming stereotyped evolution EEG patterns develop and resolve(Weiner 1982), with proposed phases of activity(Brumback and Staton 1982). Brief periods of EEG suppression or rhythmic bilateral 14-22 Hz oscillations may first emerge(Brumback and Staton 1982). Induction of bilateral poly-spike activity occurs, often with greater power on the side of the stimulation electrode in unilateral ECT(Brumback and Staton 1982). Spike/spike-and-wave complexes then occur, followed by termination within three minutes(Brumback and Staton 1982, Weiner 1982). This ictal activity may

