### 2.3.4 Inclusion/Exclusion Criteria

**Inclusion criteria:** Referral for ECT via right unilateral stimulation for treatment-resistant non-psychotic unipolar or bipolar depression, English-speaking, at least 18 years old, able to provide written informed consent.

**Exclusion criteria:** Known brain lesion or neurological illness that causes cognitive impairment, schizophrenia, schizoaffective disorder, blindness or deafness that may impair performance for cognitive testing battery, inadequate seizure duration with etomidate, defined at our institution as bilateral spike-and-wave complexes present for less than 10 seconds.

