### 2.3.6 Randomization and Blinding

A trained team member will use a computer-generated randomization algorithm among 18 potential combinations of initial cognitive task and order of study interventions. Random assignments will account for investigator-physician availability for ketamine + sham ECT sessions. The patient will be blind to the order of treatment condition. Study and clinician teams will be aware of the treatment arm at each session and maintain blinding by maintaining consistency of routine checks and monitoring before and after anesthetic induction. Thus, for all treatments sessions, patients will not be able to view the syringe during anesthetic induction. Furthermore, stimulation electrode and conducting gel will be placed on the scalp following loss and prior to return of consciousness. Post-anesthetic evaluation by anesthesiology, psychiatry, and nursing staff will be consistent across sessions.

To maximize study rigor and reproducibility, investigators evaluating study measurements for data quality and development of analytical tools will be blinded to details of the treatment intervention, whenever possible(Nuzzo 2015).

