anesthesia will be induced with ketamine, approximately 2 mg/kg, or standard of care. Following bolus of the induction agent, loss of responsiveness and evelash reflex will be confirmed. Loss of consciousness will be recorded as the first time when a subject fails to correctly respond to the command. Care adherent to the ASA guidelines will be performed regardless of treatment session. For sessions with ECT, pre-stimulation hyperventilation and assisted ventilation will also be performed. Central seizure duration will be assessed from bilateral fronto-mastoid EEG by the psychiatry team. Peripheral seizure duration will be determined through monitoring of tonic-clonic activity (Fink and Johnson 1982). During the sessions that subjects receive ECT, other drugs will also be administered according to current practice and as clinically indicated. The return of eye opening will be assessed every 30 seconds and defined for the initial time at which the patient opens his eves to verbal command. The ability to extend the thumb to verbal command ("thumbs up") will be assayed every 30 seconds. Return of responsiveness to auditory command will be defined as the first time at which the patient has squeeze his correct hand the number of times instructed via auditory commands. At this time, defined as t = 0 minutes, the subject will begin a series of cognitive and behavioral assessments, which are repeated every 30 minutes up to two hours after return of responsiveness. Patients will be permitted to take brief breaks to use the restroom and eat or drink, as necessary. At the conclusion of each treatment session, depression testing (PROMIS-CAT) and mood assessment (Self-Assessment Manikin) will be performed to assess for early improvements in mood. To assess blinding quality, the patient will be asked their impression of whether they received ECT that day. They will be discharged according to standard post-anesthesia care unit discharge criteria upon completing the last neurocognitive test battery. A study site coordinator will contact each subject within 24 hours of the study day to assess and document any adverse events.

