### 2.5.4 EEG Preprocessing and Analysis

EEGLab will be used to assess for quality and the presence of motion and eye movement artifact(Delorme and Makeig 2004). Data will undergo pre-processing with band-pass filtering from 0.1-50 Hz with 1st order Butterworth filters. Frontal channels will be assessed for eye movement artifact. Reduction of severe eye movement artifacts will employ independent component analysis approaches in EEGLab. The following analysis time epochs will be evaluated for secondary outcomes related to EEG activity: pre-ECT and post-ECT periods with either eyes open or eyes closed, the interval between anesthetic induction to and ECT stimulation, the period between stimulus delivery and cessation of ictal waveforms/spike-and-wave complexes, postictal period of EEG suppression and slowing, and both 5-minute epochs flanking the return of responsiveness to verbal command.

Spectral analysis will be performed using the Chronux Toolbox(Mitra and Bokil 2008), including five tapers, time frequency bandwidth of 3, and 6-second non-overlapping time windows. Total power and peak amplitude will be computed within the delta (0.5-4 Hz), theta (4-8 Hz), alpha (8-13 Hz), and beta (13-30 Hz) bands. Coherence and phase lag will be computed using the Chronux toolbox. Global coherence(Cimenser, Purdon et al. 2011) and permutation entropy will be computed(Bandt and Pompe 2002). Quantitative measures will be derived from spectral and time-based analyses of the ictal EEG. These measures will evaluate seizure energy, periodicity, and symmetry, as well as propagation, and termination.

In parallel to power spectral analysis, we will track the time-varying connectivity between the measured brain regions. Data will be windowed into 5-10 second epochs within which several cross-channel connectivity metrics will be computed. These measures will include the Pearson correlation, directed entropy, and Shannon mutual information. Thus, windows will manifest different 'networks', each describing the association between channels (regions) according to its respective metric. These networks will be clustered into a set of distinct motifs, or microstates, by using a k-means algorithm with least-squares error criterion. Other methods to characterize the time-varying dynamics of the observed brain activity, including those based on network control theory, will also be considered.

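### Section 2.5.3 correlates seizure length with an interval that contains the seizure, so a positive correlation cannot by itself be read as slower postictal recovery

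*Combined protocol and SAP*

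**What the plan says.** Among the secondary analyses, Section 2.5.3 gives the expectation: "We expect that the length of ECT-induced seizures will correlate with the intervals from the loss of responsiveness to the return of responsiveness". It names no test, model, significance level or null value for this relationship.

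The ends of the interval are set in Section 2.3.8 (Experimental Treatment Visits). It opens at loss: "Loss of consciousness will be recorded as the first time when a subject fails to correctly respond to the command". It closes at return: "Return of responsiveness to auditory command will be defined as the first time at which the patient has squeeze his correct hand", the squeeze being repeated as often as instructed. Appendix 1 (Study Day) requires two consecutive commands at each end instead, which shifts the ends but not their order relative to the seizure. Section 2.3.6 fixes that order: the "stimulation electrode and conducting gel will be placed on the scalp following loss and prior to return of consciousness".

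Seizure length is measured in the same sessions. Section 2.3.8 says: "Central seizure duration will be assessed from bilateral fronto-mastoid EEG by the psychiatry team". Section 2.5.4 lists as an analysis epoch "the period between stimulus delivery and cessation of ictal waveforms/spike-and-wave complexes", so the end of the seizure is available as a time point.

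Section 2.5.1 plans mixed-effects models with random effects for repeated measures and lists central seizure duration as a covariate. No section subtracts the seizure from the interval or starts a clock at its end.

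**The concern.** In an ECT session the loss-to-return interval has three parts in sequence: loss to stimulus, the seizure, and seizure end to return. Section 2.5.3 relates this total to its middle part. Only the third part is postictal recovery.

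The study is interested in that third part. Section 2.1.1 dates the postictal period from the disappearance of epileptiform EEG activity, and Section 3.4 describes the study's contribution as the effect of a seizure on consciousness and cognition once the seizure has ended. If a positive correlation were reported under 2.5.3, a reader would naturally take it to mean that longer seizures are followed by slower recovery. The same correlation would arise if every patient needed a postictal period that had nothing to do with seizure length, simply because a longer seizure takes up more of the interval.

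**Working it through.** The plan gives no figure for this correlation, so there is none to reproduce.

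**Inputs from the documents.** There are 15-20 patients with four ECT sessions each (Sections 2.6 and 2.3.7), giving 15 × 4 = 60 to 20 × 4 = 80 sessions. Commands are played every 30 s (Section 2.3.8). The background describes ictal activity "followed by termination within three minutes" (Section 2.1.2). The exclusion for inadequate seizure duration with etomidate is "bilateral spike-and-wave complexes present for less than 10 seconds" (Section 2.3.4). These limits give a scale of 10-180 s but no SD.

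**Assumptions.** SD of seizure length 10-40 s; SD of the rest of the interval 60-600 s; tests at the 5% level.

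**Algebra.** Let T be loss to return, S seizure length, and X the rest (loss to stimulus plus seizure end to return), so T = S + X. Then:

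slope of T on S = Cov(S, T)/Var(S) = 1 + Cov(S, X)/Var(S)

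- *Fixed postictal time:* X is independent of S, so the slope is 1 and r = SD_S/√(SD_S² + SD_X²).
- *Induction clock:* T is independent of S, because X shortens by one second for each extra second of seizure. Then Cov(S, X) = −Var(S), and the slope and r are both 0.
- *Slower postictal recovery after longer seizures:* Cov(S, X) > 0, so the slope exceeds 1 (provided loss-to-stimulus time is itself unrelated to S).

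**Correlation under fixed postictal time.** Example: SD_S 30 s and SD_X 120 s give 30/√(900 + 14,400) = 30/123.7 = 0.24.

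| SD_S \ SD_X | 60 s | 120 s | 180 s | 300 s | 600 s |
|---|---|---|---|---|---|
| 10 s | 0.16 | 0.08 | 0.06 | 0.03 | 0.02 |
| 20 s | 0.32 | 0.16 | 0.11 | 0.07 | 0.03 |
| 30 s | 0.45 | 0.24 | 0.16 | 0.10 | 0.05 |
| 40 s | 0.55 | 0.32 | 0.22 | 0.13 | 0.07 |

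**Chance of p < 0.05 against zero (Fisher z).** For SD_S 30 s and SD_X 120 s it is 14% with 15 patients and 18% with 20 (one value each). It is 46% with 60 sessions and 58% with 80 if sessions are treated as independent. Over the whole table it is 5-73% with 20 patients and 5% to about 100% with 80 independent sessions.

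**Simulation.** 20 patients × 4 sessions, intraclass correlation 0.5, return rounded up to a 30 s grid, SD_S 20 or 30 s, SD of the remaining time 60-300 s:

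| Truth | Slope of T on S | r(S, T) | Rejection, patient means | r(S, seizure end to return) |
|---|---|---|---|---|
| Fixed postictal time | 0.99 to 1.05 | 0.07 to 0.40 | 7-48% | −0.003 to 0.004 |
| Induction clock | −0.01 to 0.06 | −0.003 to 0.004 | 4-5% | −0.06 to −0.43 |

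The last column shows that restarting the clock at seizure end is not neutral. It removes the overlap under fixed postictal time and creates a negative correlation under an induction clock.

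**The case against.** The strongest reply is that containment alone forces nothing. Each session begins with an anesthetic induction, and Section 2.5.2 itself speaks of seizures adding to recovery from anesthesia. If return is driven by anesthetic washout and the seizure ends first, the interval is unrelated to seizure length and the planned test behaves properly. This stands. A reader might infer that the positive correlation is guaranteed by construction; the documents do not support that, because they do not say which clock governs return.

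Second, the heading in 2.5.3 refers only to return of responsiveness, not to postictal recovery. Under fixed postictal time each extra second of seizure does delay return by one second, and loss-to-return measures that total delay. It is also the interval used in the primary responsiveness analysis, where sham sessions have no seizure end. So it would go too far to say that the planned analysis cannot answer its question, or that the interval should be discarded. What remains is that Sections 2.1.1 and 3.4 show interest in the period after the seizure, and 2.5.3 does not separate the two readings.

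Third, the size is uncertain. Both SDs are assumed, and treating sessions as independent departs from 2.5.1. At an SD of 300 s or more for the rest of the interval, the correlation is at most 0.13. A reader might infer a large false-positive rate; the documents establish none.

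Adjusting for central seizure duration, as 2.5.1 allows, does not answer the point: in this analysis seizure duration is the predictor of interest, and its coefficient carries the overlap.

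**Conclusion.** The point holds as a limit on interpretation. The seizure lies inside the loss-to-return interval by definition, and 2.5.3 states no null value. A positive correlation there cannot distinguish longer seizures slowing postictal recovery from longer seizures simply occupying more of the interval. Under fixed postictal time the expected slope is 1 s per s. This assumes that both remaining parts of the interval are unrelated to seizure length. Under a pure induction clock it is about 0.

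The size is not fixed by the documents. Under the assumed SDs the correlation with fixed postictal time lies between about 0.02 and 0.55, and at the low end it would rarely be detected with 15-20 patients. This is a secondary analysis in a study that Section 2.5 calls exploratory; no primary outcome or sample size depends on it. The change is worth making because it is cheap and prevents a specific misreading.

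**What to change.** In 2.5.3, for ECT sessions only:

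- Fit a mixed model with a patient random effect, as in 2.5.1, and report the slope of loss-to-return time on central seizure duration with its 95% CI. Keep both in untransformed seconds for this purpose, since the reference value of 1 has no meaning after a transformation.
- Read the slope against two values: 0 (induction clock) and 1 (fixed postictal time). Take only a slope above 1, with its CI, as evidence of slower postictal recovery. A positive slope or correlation alone is not such evidence.
- Report the time from EEG seizure end to return of responsiveness alongside, not instead. It drops the procedural loss-to-stimulus time. State its null (no relation between postictal time and seizure length) and note that it is biased negative if return depends only on time since induction.

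The cost is one or two sentences. Seizure duration, the stimulus-to-cessation epoch and the return time are already planned, so no new data are needed. The reported association may look weaker than the correlation now expected.

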# 2.3 Design and Participants:

# 2.3.1 Study Design

We propose over three years to randomize fifteen to twenty patients with refractory depression to one of three treatments in two consecutive weeks of an ECT treatment cycle. Each patient will complete seven study visits. The first visit will be conducted during the dose-charge titration ECT treatment. Following the titration visit, there will be six separate experimental treatments per patient in two blocks of three, with a random sequence in each block (Figure 1). During these six visits, patients will be randomized to receive one of three treatments, all of which are likely to have efficacy in treating refractory depression: 1) ketamine alone, 2) ketamine plus ECT, or 3) standard of care anesthetic plus ECT.

**Figure 1:** Block randomized, repeated measures, crossover experimental design for reconstitution of consciousness and cognition following electroconvulsive therapy (ECT) and general anesthesia. K, ketamine; E, etomidate, Rx, treatment.

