### 2.7. Management of Intercurrent Events

### 2.7.1 Cross-over, repeated measures

18

The study design has a built in cross-over, repeated measures to allow patients to serve as their own control and to experience each of the treatments twice.

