Patient satisfaction will be monitored throughout the study. Ketamine may improve the efficacy of ECT and recovery of cognitive function following ECT. Patients may benefit from the additional EEG monitoring in the postictal period during which non-convulsive status epilepticus is rarely manifested. Patients will be withdrawn if discontinuation is in the best interest of the patient or if the patient requests withdrawal or removal of treatment blinding. In the event that a patient's condition significantly worsens and requires additional or different interventions from those allocated in the study, the patient will be released from the study and data collection will be discontinued. Participants are given a satisfaction survey to be returned by mail following the last study session(Sienaert, De Becker et al. 2005).

**Participant Satisfaction:** During the follow-up phone call for the last study session, participants will be asked about their satisfaction in the study(Sienaert, De Becker et al. 2005).

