### **Assessment of Patient Satisfaction**

1. Did you have any side effects or problems after receiving treatments? Please indicate after which treatment these side effects occurred (check all that apply).

	1 st	2 nd	3 rd	4 th	5 th	6 th	Yes, but not sure when
Nausea							
Vomiting							
Confusion							
Bruising or tenderness at IV site							
Fever							
Headache							
Weakness							
Memory loss							
Agitation							
Hallucinations							
Jaw pain							
Nightmares							

Other:				

The following items refer to your experience throughout the entire study. Please rate how well you agree with each statement.

		Strongly agree	Agree	Neutral	Disagree	Strongly disagree
2.	I was satisfied with my care.					
3.	Overall, I felt comfortable throughout the study.					
4.	I learned about consciousness and cognition by participating.					
5.	I was well compensated for this study.					
6.	I am satisfied with my interactions with the study team.					
7.	I would participate in this study again.					
8.	My condition improved after completing the treatments.					

- 9. What was the most physically uncomfortable or distressing part of the study?
  - $\Box$  Consent
  - □ Screening questionnaires (performed in the days or weeks before treatment)
  - $\Box$  EEG cap
  - □ Morning before treatment
  - $\Box$  Recovery from treatment

If yes, please indicate which (check all that apply):

- $\Box$  1st
- $\square$  2nd
- $\Box$  3rd
- $\Box$  4th
- $\Box$  5th
- $\Box$  6th
- □ No period was particular uncomfortable or distressing
- Other:

10. How physically uncomfortable or distressing was the experience selected in the previous question?

- □ Extremely
- $\Box$  A lot
- □ A little
- $\Box$  Not very
- $\square$  N/A
- 11. What did the study team do well?
- 12. Which aspects could the study team improve?

\_\_\_\_\_

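### Satisfaction is to be compared between the three treatments, but each patient rates it only for the study as a whole, after receiving all three

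*Combined protocol and SAP*

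**What the plan says.** Under Treatment Satisfaction, section 2.5.3 states: "We expect satisfaction to be greatest for ketamine + ECT, followed by ketamine + sham ECT", and places etomidate + ECT last. It gives no model or test for this.

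On exposure, section 2.3.1 says "there will be six separate experimental treatments per patient in two blocks of three, with a random sequence in each block", and section 2.7.1 says the design is meant "to allow patients to serve as their own control and to experience each of the treatments twice".

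On measurement, section 2.8 gives two routes. One is a postal survey: "Participants are given a satisfaction survey to be returned by mail following the last study session". The other is a call: "During the follow-up phone call for the last study session, participants will be asked about their satisfaction in the study". In the survey form (Appendix, Assessment of Patient Satisfaction), the rating items 2–8 are introduced by "The following items refer to your experience throughout the entire study". Only item 1 (side effects) and item 9 (the most uncomfortable or distressing part) let the patient point to a session number. Table 1 lists no satisfaction item at baseline or at 0, 30, 60 or 90 minutes. The questions at the end of sessions 2–7 ask only whether the patient thinks ECT was given and whether it hurt.

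**The concern.** The hypothesis in 2.5.3 concerns differences between treatments, so it needs ratings that can be attributed to a treatment. The ratings described are attributable only to a patient's whole participation, and every completer's participation contains the same mix of treatments. If so, a listed secondary analysis has no satisfaction data behind it. A larger sample would not help, and nothing done at the analysis stage would. The crossover was chosen for its within-patient comparisons, yet for this outcome it would deliver none.

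**Working it through.** The plan states no sample size, power or precision for satisfaction, so there is no figure to reproduce. The question is whether the treatment contrasts are estimable.

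**Inputs**
- Treatments: 3 (section 2.3.1).
- Sessions per patient: 6, in two blocks of three (section 2.3.1).
- Exposure of each completer: every treatment twice (section 2.7.1).
- Patients: 15–20 (section 2.6).
- Satisfaction ratings: at the end only, for the whole study (section 2.8 and survey items 2–8).

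**Ratings as planned**

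There are 3! = 6 orders per block, hence 6 × 6 = 36 possible two-block sequences. Under all of them the exposure counts for (ketamine + ECT, ketamine + sham, etomidate + ECT) are (2, 2, 2). Let the whole-study rating of patient i be

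y_i = μ + 2a + 2b + 2c + error,

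where a, b and c are the treatment contributions. Every row of the treatment design matrix is (2, 2, 2), so its rank is 1, and it stays 1 when an intercept is added. A contrast is estimable only if it lies in the row space, that is, if it is a multiple of (2, 2, 2). The contrasts (1, −1, 0), (1, 0, −1) and (0, 1, −1) are each orthogonal to that vector; for example 2 − 2 + 0 = 0. None of the three is estimable. A numerical rank check gave the same answer for 15, 20 and 36 patients. Only the sum a + b + c is seen, and it is inseparable from μ.

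**One rating per session**

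Now let y_ij = patient effect + session-position effect + treatment effect + error.
- Ratings: 15 × 6 = 90 to 20 × 6 = 120.
- Per treatment: 15 × 2 = 30 to 20 × 2 = 40, two from each patient.
- In the rank check, with sequences drawn at random for 15 and for 20 patients, all three pairwise contrasts were estimable after allowing for patient and session position.

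**Could another planned measure stand in?**
- Survey items 1 and 9 can be linked to treatment through the randomization list, but they record tolerability recalled at the end. Item 1 even provides a column for patients who cannot say when a side effect occurred.
- The mood manikin is completed at every session, but it asks about mood at that moment. Section 2.5.3 expects a different order for mood and depression (etomidate + ECT above ketamine + sham) from that for satisfaction (the reverse), so the plan itself treats these as different quantities.

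**The case against.** The strongest case on the other side has four parts.

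1. **Other text and data.** Section 2.8 also says satisfaction will be followed over the course of the study. Each session ends with a question on pain, and side effects are asked by session number. So there is some patient-experience data by treatment. This stands as far as it goes: a descriptive comparison of tolerability is possible. But the sentence in 2.8 names no instrument or schedule, and pain and side effects are not satisfaction.

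2. **Low status.** Satisfaction is missing from the Primary and Secondary Outcomes section (2.4.7.1). The synopsis lists it last, as an overall outcome, which the survey fits. The study calls itself exploratory. All true, and this limits the consequence. Exploratory status relaxes demands on power and error control; it does not supply data for a stated comparison.

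3. **Other routes to a contrast.** Treatment order differs between patients, so an effect of sequence on the final rating could be modelled. Reading it as a treatment effect needs an untested assumption, such as the last session dominating the rating. Patients who stop early may have unequal exposure, but comparing them is not a randomized comparison, and the survey is tied to the last session.

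4. **Timing of a new item.** At 90 minutes cognition may still be impaired, and a single new item is unvalidated. This is a fair caution, but Table 1 already schedules the PROMIS-CAT and the mood manikin, both self-rated, at 90 minutes. It is also fair that the cognitive model in 2.5.1 does not carry over unchanged, because satisfaction would be one ordinal response per session with no time course within it.

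**Conclusion.** The point holds. As written, the plan yields at most 15–20 whole-study ratings and no estimable contrast among the three treatments, at any sample size. This rests on two readings: that completers receive each treatment exactly twice, and that the end-of-study survey and phone call are the only satisfaction measures. The documents support both. If the sponsor intends session-level ratings under the general statement in 2.8, they need to be specified. The count of 15–20 assumes that every survey is returned. The contrast of 15–20 with 90–120 ratings shows what would be collected, not how precise the comparison would be; the documents give no variance for satisfaction. The primary outcomes are untouched, but the gap must be closed before patients are treated: patients are blind to treatment order and cannot be relied on to rate six sessions separately afterwards.

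**What to change.** Choose one of two routes.

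- **Keep the comparison.** Add one 5-point satisfaction item to the 90-minute questionnaire at Visits 2–7. Place it beside the blinding question in Table 1 and ask it first, so that the patient's guess about ECT does not colour the rating. Analyse it with a mixed model (an ordinal form is natural) with treatment and session position as fixed effects and patient as a random effect. Report the three pairwise differences with confidence intervals. Keep the end-of-study survey for overall satisfaction.
- **Drop the comparison.** Delete the between-treatment satisfaction hypothesis from 2.5.3 and report the end-of-study survey descriptively, in line with the synopsis outcome.

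The first route costs a few seconds of patient time per session, a line on the case report form and a minor amendment; its limitation is a single unvalidated item given during recovery. The second costs only an edit to the text. Under either route, section 2.8 should say what following satisfaction during the study consists of.
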